## 5.6 Study Completion and Discontinuation

### 5.6.1 Study completion and post-study treatment

At the end of the study, all patients will return for the final end of study (EOS) visit (Visit 299) and be asked to return the remaining study drug. The study will be completed once all assessment up to the last participant reaches Month 36 (Visit 299) **or** a recommendation is made by the DMC to prematurely stop the study.

The study will be complete when the last patient enrolled has completed their last visit.

The investigator must provide follow-up medical care for all patients who are prematurely withdrawn from the study, or must refer them for appropriate ongoing care.

A patient will be considered to have completed the study when the patient has completed the last visit planned in the protocol.

### 5.6.2 Discontinuation of study treatment

Discontinuation of study treatment occurs when study drug is stopped earlier than the protocol planned duration, and this can be initiated by either the patient or the investigator.

The investigator must discontinue study treatment for a given patient if he/she believes that continuation would negatively impact the risk/benefit of trial participation.

Study treatment must be discontinued under the following circumstances:

- Patient wish
- Pregnancy (see [Section 6.5.9](#) and [Section 7.7](#))
- Use of prohibited treatment as per recommendation in [Table 5-3](#)
- Any situation in which study participation might result in a safety risk to the patient

However; study treatment discontinuation does not constitute withdrawal from the study and should not lead to the patient being withdrawn from the study.

Every effort should be made to complete end of treatment (EOT) assessments within 3 months of the last study drug dose for patients who have discontinued study drug permanently. For patients who terminate the study early, they are expected, and should be encouraged, to attend all the protocol specified study visits and perform all measurements as stipulated in the visit schedule ([Table 6-1](#)) and remain in follow up for the duration of the trial.

If they fail to return for these assessments for unknown reasons, every effort should be made to contact them. If the patient cannot or is unwilling to attend any visit(s), the site staff should maintain regular telephone contact with the patient, or with a person pre-designated by the patient. This telephone contact should preferably be done according to the study visit schedule.

The investigator must contact the IRT to register the patient's discontinuation from study treatment and must determine the primary reason for the patient's premature discontinuation of study treatment and record this information on the Dosage Administration eCRF.

The emergence of the following circumstances will require permanent study drug discontinuation:

- Withdrawal of informed consent
- Investigator thinks that continuation would be detrimental to the patient's well-being
- Suspected occurrence of angioedema. A patient with any signs or symptoms of clinically significant angioedema should be thoroughly evaluated by the investigator

Use of an open label ACEi, ARB or renin inhibitor will require temporary or permanent discontinuation (study drug may be restarted once these medications are stopped).

Study drug may be discontinued at the investigator's discretion if any of the following occurs:

- Any severe suspected drug-related AE
- Any other protocol deviation that results in a significant risk to the patient's safety.

The appropriate personnel from the site and Novartis will assess whether study drug should be permanently discontinued for any patient whose treatment code has been broken inadvertently for any reason.

If study drug discontinuation occurs because treatment code has been broken, please refer to [Section 5.5.9](#).

The details about study assessment to be completed for patients who permanently discontinued study drug are provided in [Section 6](#).

### **5.6.3 Withdrawal of informed consent**

Patients/subjects may voluntarily withdraw consent to participate in the study for any reason at any time. Withdrawal of consent from the study is defined as when a patient:

- Does not want to participate in the study anymore

and

- Does not want any further visits or assessments

and

- Does not want any further study related contacts

and

- Does not allow analysis of already obtained biologic material

In this situation, the investigator must make every effort (e.g. telephone, e-mail, letter) to determine the primary reason for the patient's decision to withdraw his/her consent and record this information.

Study treatment must be discontinued and no further assessments conducted, and the data that would have been collected at subsequent visits will be considered missing.

Further attempts to contact the patient are not allowed unless safety findings require communicating or follow-up.

All efforts should be made to complete the assessments prior to study withdrawal. A final evaluation at the time of the patient's study withdrawal should be made as detailed in [Table 6-1](#).

#### **5.6.4 Loss to follow-up**

For subjects whose status is unclear because they fail to appear for study visits without stating an intention to discontinue or withdraw, the investigator should show "due diligence" by documenting in the source documents steps taken to contact the subject, e.g. dates of telephone calls, registered letters, etc. A patient cannot be considered as lost to follow-up until the time point of his/her scheduled end of study visit has passed.

#### **5.6.5 Early study termination by the sponsor**

The study can be terminated by Novartis at any time for any reason. This may include reasons related to the benefit-risk assessment of participating in the study, practical reasons, or for regulatory or medical reasons (including slow enrolment). Should this be necessary, the patient must be seen as soon as possible and treated as a prematurely withdrawn patient. The investigator may be informed of additional procedures to be followed in order to ensure that adequate consideration is given to the protection of the patient's interests. The investigator will be responsible for informing the Institutional Review Board/Independent Ethics Committee (IRBs/IECs) of the early termination of the trial.

### **6 Visit schedule and assessments**

Table 6-1 lists all of the assessments and indicates with an "x" when the visits are performed.

Patients/subjects must be seen for all visits on the designated day, or as close to it as possible. Missed or rescheduled visits should not lead to automatic discontinuation.

[figure not shown]
After randomization, study drug discontinuation (permanent or temporary) for any reason does not constitute withdrawal from the study and should not lead to the patient being withdrawn from the study. Patients who discontinue study drug should be requested to return for an End of Treatment visit (EOT) in which all of the assessments outlined in Table 6-1 will be performed.

Patients who prematurely discontinue the study for any reason should be scheduled for a visit as soon as possible, at which time all of the assessments listed for the end of study visit will be performed. At the end of study visit, all dispensed investigational product should be reconciled and the adverse event and concomitant medications reconciled on the CRF.

Every effort should be made to complete end of treatment (EOT) assessments within 3 months of the last study drug dose for patients who have discontinued study drug permanently. Patients who terminate study drug early are expected, and should be encouraged to, attend all the remaining protocol specified study visits and perform all measurements as stipulated in the visit schedule (Table 6-1).

For EOT / End of Study (EOS) visit, the PET and MRI scans will only be performed if prior scans were performed more than twelve months ago. The CCB, [REDACTED] FAQ, [REDACTED] assessments will only be performed if prior assessments were performed more than three months ago.

Documentation of attempts to contact the patient should be recorded in the source documentation.

After identifying a potential patient, an informed consent form (ICF) must be signed by the patient before performing all study-related screening. The AE and serious adverse event (SAE) reporting period begins at the time the ICF is signed.

A Visit 199 (end of run-in visit) will be completed for all patients who enter the treatment run-in epoch. For patients who discontinue during the treatment run-in epoch or who are not able to be randomized due to safety reasons, Visit 199 will be their discontinuation visit.

For patients that will be randomized, Visit 199 will be their end of treatment run-in disposition visit.

In addition, NYHA class assessment, concomitant medications, review of inclusion/exclusion criteria, drug accountability, AE/SAE, should also be done at Visit 199. To allow patients to be randomized at Visit 201, patients should have a PET scan scheduled at Visit 199 (for all patients participating in the substudy) since it may take up to 5 days following the scan for the brain images to be centrally read. PET scan should be scheduled only after confirming that the patient fulfills all inclusion and exclusion criteria, safety criteria and is eligible for randomization.

Following completion of the PET scan, all patients will be randomized at Visit 201. The CogState Cognitive Battery, FAQ, APOE4, and plasma beta-amyloid assessments will all be performed at Visit 201.

End of run-in assessments (Visit 199) and assessments for randomization (Visit 201) are reflected at Visit 199/201 in [Table 6-1](#).

Visit 201 will be considered the reference visit for all study visits during the randomized treatment epoch. Regardless of the occurrence of any unscheduled visits, scheduled visits should be performed within the specified timeframe in relation to Visit 201 as outlined in [Table 6-1](#). If a visit is completed earlier than scheduled or postponed, it should not result in the next visit being brought forward or postponed.

[figure not shown]
Patients will have regular clinic visits performed for the first 6 months (up to and including Week 26). Thereafter, patients will have clinic visits alternating with telephone contact visits every 3 months.

Patients/subjects will be contacted for safety evaluations during the 30 days following the last administration of study treatment.

**Table 6-1 Assessment schedule**

Epoch		Screening	Active Run-in			Randomized Treatment													
			101	102	103	199/ 201 ††	202	203	204 	205	206 	207	208 	209	210  , 212 	211	EOT 	UNS	299  End of Study
Visit		1																	
Week (w)		-11/-7	-8/-4	-6/-3	-4/-2	0	13	26	39	52	65	78	91	104	117, 143	130			156
Month							3	6	9	12	15	18	21	24	27, 33	30			36
Informed consent	DS	X																	
Inclusion/Exclusion criteria	DS	X	X	X	X	X													
Safety monitoring criteria	DS	X		X 	X	X													
Demography/Relevant Medical history/Current medical conditions	DS	X																	
Heart Failure/ Smoking history/Alcohol history	DS	X																	
Echocardiography 	DS	X																	
Concomitant medications	DS	X	X	X	X	X	X	X	X	X	X	X	X	X	X	X	X	X	X
NYHA classification (HF signs/symptoms)	DS	X				X		X		X		X		X		X	X	X	X
Florbetapir  F PET scan	DS					X A						X					X 		X 
MRI Scan 	DS	X										X					X 		X 
Cognitive Assessment (CogState Battery) 	DS	X			X	X A		X		X		X		X		X	X		X

[figure not shown]
Epoch		Screening	Active Run-in			Randomized Treatment														
			101	102	103	199/ 201 ††	202	203	204 	205	206 	207	208 	209	210  , 212 	211	EOT 	UNS	299  End of Study	
Visit		1																		
Week (w)		-11/-7	-8/-4	-6/-3	-4/-2	0	13	26	39	52	65	78	91	104	117, 143	130			156	
Month							3	6	9	12	15	18	21	24	27, 33	30			36	
Functional Activity Questionnaire (FAQ) 	DS	X				X A		X		X		X		X		X	X		X	
Physical Exam 	S	X		X	X	X		X		X		X		X		X	X	X	X	
Height	DS	X																		
Weight	DS	X				X		X		X		X		X		X	X	X	X	
Abbreviated laboratory evaluations 	DS			X 	X		X	X				X				X		X		
Local laboratory 				(X)	(X)	(X)												(X)		
Vitamin B12 and Folate	S	X																		
Thyroid stimulating hormone	S	X																		
FSH 	S	X																		
APOE4 genotyping/ [REDACTED] 	DS					X														
NT-proBNP 	DS	X																		
Dispense study medication	S		X	X	X	X A	X	X		X		X		X		X		(X)		
Contact IVRS	S	X	X	X	X	X	X	X	X	X	X	X	X	X	X	X	X	X	X	X
Drug Accountability	DS			X	X	X	X	X		X		X		X		X	X	(X)	X	
Plasma $\beta$ -amyloid 	DS	X				X A	X			X				X			X		X	

Epoch		Screening	Active Run-in			Randomized Treatment													
			101	102	103	199/ 201 ††	202	203	204 	205	206 	207	208 	209	210  , 212 	211	EOT 	UNS	299  End of Study
Visit		1																	
Week (w)		-11/-7	-8/-4	-6/-3	-4/-2	0	13	26	39	52	65	78	91	104	117, 143	130			156
Month							3	6	9	12	15	18	21	24	27, 33	30			36
Screening disposition	DS	X																	
Run-in disposition	DS					X													
Treatment disposition	DS																X		X

DS= assessment to be recorded in clinical database; S= assessment to be recorded on source document; UNS = unscheduled visit; EOT=(end of treatment); Patients will be contacted for safety evaluations during the 30 days following the last administration of study treatment (X) = optional assessment  
††= Visit 199/201 (end of treatment run-in) will be completed for all patients who enter the treatment run-in epoch. For patients who discontinue during the treatment run-in epoch, Visit 199 will be their discontinuation visit. For patients that have completed a PET scan and are randomized at Visit 201, procedures marked as 'λ' will be performed.  
 Telephone visit  
 Female subjects only with oophorectomy without hysterectomy.  
 If patient discontinues study drug permanently these assessments should be done within 3 months of last dose.  
 Qualifying LVEF measurements/documentation will be based on locally obtained most recent assessments performed ≤ 6 months prior to Visit 1. If an EF assessment performed ≤ 6 months prior to Visit 1 is not available, an echo must be performed during the Screening epoch.  
 The PET and MRI scans will be done at EOT/EOS only if prior scans were performed more than twelve months ago.  
 The CCB, ████████ FAQ, ████████ will be done at EOT/EOS only if prior assessments were performed more than three months ago  
 Visit 299 (end of study visit) will be completed for all patients that enter the randomized treatment epoch.  
 Serum potassium and eGFR to be performed at Visit 102 only if patient enters the run-in epoch at Visit 101.  
 Complete physical exam will be performed at Screening Visit 1, EOS, and EOT, all other visits will be a short physical exam.  
 Abbreviated laboratory assessments includes: serum creatinine, potassium and eGFR  
 Serum potassium and serum creatinine for eGFR. If patient enters run-in period at Visit 102, laboratory evaluation at this visit is not required  
 Cognitive assessments should ideally be administered by the same assessor in a quiet environment and prior to any other clinical assessments scheduled during the day  
 If the PG sample is not collected at Visit 201, it may be obtained at any visit thereafter and is only analyzed in patients consenting to the PG analysis  
 NT-proBNP will be analyzed in serum and collected as part of the clinical chemistry sample  
 MRI scans at Visit 207 and Visit 299 are performed only in patients participating in the PET substudy  
 Plasma β-amyloid will be assessed only in patients participating in the PET substudy

Epoch		Screening	Active Run-in			Randomized Treatment													
Visit		1	101	102	103	199/ 201 ††	202	203	204 	205	206 	207	208 	209	210  , 212 	211	EOT 	UNS	299  End of Study
Week (w)		-11/-7	-8/-4	-6/-3	-4/-2	0	13	26	39	52	65	78	91	104	117, 143	130			156
Month							3	6	9	12	15	18	21	24	27, 33	30			36
AE – adverse event; APOE4 – Apolipoprotein E ε4 allele; [REDACTED]; EOT – end of treatment; FSH – follicle stimulating hormone; IVRS – interactive voice recognition system; [REDACTED]; NT-proBNP – N-terminal pro-brain natriuretic peptide; NYHA – New York Heart Association; PET – positron emission tomography; SAE – serious adverse event																			

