#### 3.1 Study design

This study is a multi-center, randomized, double-blind, parallel group, active comparator trial designed to evaluate the overall effect of LCZ696 compared to valsartan on cognitive function as assessed by a comprehensive cognitive battery in patients with HFpEF (Figure 3-1). The study population will consist of patients  $\geq 60$  years of age with chronic symptomatic HF (NYHA class II-IV) and a left ventricular ejection fraction (LVEF)  $>40\%$ . Patients will be randomized in a 1:1 fashion to either LCZ696 200 mg bid or valsartan 160 mg bid.

Cognitive function will be assessed at baseline and every six months up to 3 years by a comprehensive cognitive battery, and MMSE will be assessed annually. Patients scoring  $<24$  on the MMSE scale during screening will be excluded from the study. Patients will be stratified based on age ( $< 75, \geq 75$  years), MMSE score ( $< 28, \geq 28$ ), and if participating in the PET imaging substudy, amyloid status (amyloid positive/negative). APOE4 is a strong predictor of cognitive impairment (Lim et al 2015) and A $\beta$  accumulation. Therefore, patients will be genotyped for APOE4 allele status.

[figure not shown]
The study will also evaluate the impact of LCZ696 therapy compared to valsartan on  $\beta$ -amyloid deposition in the brain using florbetapir  $^{18}\text{F}$  PET imaging in a subset of patients. PET imaging requires specialist centers experienced in the technique that are in close proximity to a radiopharmaceutical production facility, thus a subset of centers will be selected as PET centers. To ensure high quality of imaging data, PET imaging will be conducted in all eligible patients at selected PET capable centers. Amyloid PET imaging will be performed at randomization, at 18 months, and at 3 years (EOS Visit). If a patient permanently discontinues treatment prior to 3 years, a PET scan should be done at the end of treatment visit (EOT visit) if a prior scan was performed more than twelve months ago. End of study (EOS) scan will not be required if EOT scan is performed within 12 months of end of study visit. All PET scans will be evaluated centrally.

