Each of the cognitive tests in the CCB will be administered electronically to patients using a computer or tablet in an area suitable for testing without distraction. While subjects themselves perform the tests on the computer or tablet, this performance is guided by an appropriately trained and credentialed rater. The electronic administration ensures standard administration of tests and also means that the CCB can be administered with high fidelity by non-expert but appropriately trained clinical staff (e.g., research assistants or nurses). Assessment with the CCB should take place in a location free from distraction and all site staff nominated to administer the CCB will undergo specific training to ensure that they understand the testing software, the testing processes, the administration of each test and the transfer of test results to CogState. Further details about CogState battery will be provided in CCB manual.

The cognitive test battery will be administered at Screening visit (Visit 1), Visit 103, and randomization visit (Visit 201), and throughout the duration of the study at 6 month intervals, including the end of treatment visit (if prior assessments were performed more than three months ago) and end of study visit (Visit 299).

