#### **6.4.4 Instrumental activities of daily living as assessed by functional activity questionnaire**

The functional activities questionnaire will be used as a standardized assessment of activities of daily living. This questionnaire is typically used to distinguish normal subjects from subjects with mild to moderate cognitive impairment. FAQ evaluation will be performed at Screening visit (Visit 1), randomization visit (Visit 201), at 6 months (Visit 203), 12 months (Visit 205), 18 months (Visit 207), 24 months (Visit 209), 30 months (Visit 211), end of treatment visit (if prior assessments were performed more than three months ago), and at 36 months end of study (Visit 299). The changes from baseline to 3 years will be analyzed.

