In addition, to assess the sensitivity of the analysis results to the MAR assumption used in the multiple imputation for primary analysis method, a tipping point analysis will be performed on the change from baseline in SUVr which assumes that missing values after death, HF hospitalization and stroke are missing not at random (MNAR). This analysis will follow the same procedure as described in [section 2.5.5](#) for the primary endpoint, with the exception that the imputations under MAR are obtained from a regression based imputation as described in the primary analysis method of this endpoint ([Section 2.7.1](#)). The analysis will be repeated for varying penalty factors in a range between 1 and 1.6.

[figure not shown]
If convergence issue arises in any of above described supportive analyses, the handling approach described in [Section 2.7.1](#) will be used to address the convergence issue.

[figure not shown]
Furthermore, to assess the sensitivity of the analysis results to the randomization stratification that is done incorrectly due to transcription error or inconsistent site and central reviewer readings, analysis described in [Section 2.7.1](#) will be repeated using the final data entered in the clinical database, instead of the stratification factors based on IVR system.

[figure not shown]
To address missing assessments due to COVID-19 pandemic, the analysis mentioned in [Section 2.7.1](#) will be repeated using PET substudy set with a wider assessment window extending from 6 months to 9 months for assessments that are scheduled to take place starting Mar 1, 2020 and onwards. This also applies to the data excluded from analysis if assessment is done more than 9 months after last study drug intake instead of 6 months.

[figure not shown]
All analyses will be performed in patients in the Safety set who participate in the PET image substudy and with non-missing baseline, including ‘on-treatment’ data only. On-treatment data refer to the SUVr values obtained while patients are on-study-medication (regardless of treatment interruption), or within defined window in each supportive analysis (six months or nine months) after the final study drug intake date.

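### Protocol Table 6-1 footnote 6 and Section 6 let the Week 156 cognitive battery and FAQ be skipped after a recent assessment, whereas Sections 6.4.1 and 6.4.4 attach that condition to the EOT visit only

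*Protocol*

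**What the plan says.** **CCB and FAQ, conditional at both visits.** Protocol Table 6-1, footnote 6, is attached to the CogState and FAQ rows and says these assessments "will be done at EOT/EOS only if prior assessments were performed more than three months ago". In Section 6, a sentence naming both the EOT and the end-of-study (EOS) visit is followed by the statement that the CCB and FAQ "assessments will only be performed if prior assessments were performed more than three months ago".

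**CCB and FAQ, conditional at EOT only.** Section 6.4.1 lists the six-monthly batteries, "including the end of treatment visit (if prior assessments were performed more than three months ago) and end of study visit (Visit 299". Section 6.4.4 lists the FAQ visits, ending with "end of treatment visit (if prior assessments were performed more than three months ago), and at 36 months end of study (Visit 299". In both, the bracketed condition belongs to EOT, and Visit 299 has none.

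**PET and MRI.** Footnote 5 reads "The PET and MRI scans will be done at EOT/EOS only if prior scans were performed more than twelve months ago". Section 6 agrees ("the PET and MRI scans will only be performed if prior scans were performed more than twelve months ago"), and so does Section 6.5.1 for PET. Section 3.1 has a narrower trigger for PET: "End of study (EOS) scan will not be required if EOT scan is performed within 12 months of end of study visit".

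**Analysis.** Protocol 9.4.2 and SAP 2.5.2 draw the primary conclusion from the Week 156 contrast. On-treatment data run to three months after the last dose (Protocol 9.4.2, SAP 2.1.1). The supportive FAS analysis uses all available data.

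**The concern.** Visit 299 supplies the primary endpoint and the 3-year FAQ endpoint. A site working from the assessment table can properly leave both out for some patients, while a site working from Sections 6.4.1 and 6.4.4 would do them. Collection of the primary endpoint would then depend on which page the site reads.

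The patients exposed are mainly those who took study drug for nearly three years and were still attending. Their Week 156 score could have been observed. Under the footnote it becomes a missing value handled under missing at random, and it is lost to the FAS analysis as well.

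**Working it through.** **1. The plan's own figure.** Inputs from Protocol 9.8.1 and 9.8.3: d = 0.3, two-sided 95% CI, 80% probability, 180 per group, 30% loss, 520 randomized.
- n per group = 2 × (1.96 + 0.842)² / 0.3² = 175, against 180 stated.
- Power at 180 = Φ(0.3 × √(180/2) − 1.96) = Φ(0.886) = 0.812 (0.810 with the noncentral t).
- 360 / 0.70 = 515, against 520 stated; 520 × 0.70 = 364, or 182 per group.

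The sample size reproduces.

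**2. Patients on schedule.** The last battery before Week 156 is at Week 130, and 156 − 130 = 26 weeks, about six months. The condition is met and the Week 156 assessment is done.

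**3. When the waiver applies.** Taking three months as 13 weeks, Week 156 is skipped if a prior battery falls at about 156 − 13 = Week 143 or later. There are two routes:
- *An EOT battery.* After an on-schedule Week 130 battery, an EOT battery is itself done only once 13 weeks have passed, that is after 130 + 13 = Week 143. So any EOT battery done between then and Week 156 triggers the EOS waiver.
- *A late Week 130 battery.* It would have to be about 13 or more weeks late. Section 6 says a postponed visit does not move the next one, so this is possible but should be rare.

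**4. A worked patient.** Last dose at Month 34, EOT visit at Month 34.5.
- At EOT the Month 30 battery is 4.5 months old, so the EOT battery is done.
- At Month 36 that battery is 1.5 months old, so footnote 6 cancels the CCB and FAQ.
- The cancelled score would have been 2 months after the last dose, inside the three-month on-treatment window.

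**5. Whether the analysis recovers the value.** Protocol 9.4.3 permits, without requiring, remapping of an unscheduled value within three months to a missing scheduled visit. An EOT visit is a protocol-defined visit, so it is unclear that this applies. SAP 2.5.3 has no such rule, and SAP Table 2-3 lists only the scheduled weeks for the GCCS analyses. For SUVr, by contrast, SAP Table 2-4 expressly admits other post-baseline measurements up to six months after the last dose.

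**6. How many.** The documents give no count. Assuming the 30% loss is spread over 36 months, those leaving in the last three months are:
- evenly spread: 0.30 × 3/36 × 520 = 13;
- exponential, r = −ln(0.7)/36: exp(−33r) − exp(−36r) = 2.1%, and 0.021 × 520 = 11.

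This is a ceiling for scores the primary analysis could have used. Someone who stopped somewhat before Week 143 but had the EOT visit after it would lose only a FAS value and is not in this count.

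**7. Power if the loss were extra.** Treating each lost Week 156 value as a lost patient, 182 per group gives 0.816, and a further 2% loss gives 0.809. This is a worst case, because the repeated-measures model still uses the earlier visits.

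**The case against.** **The loss is already budgeted.** Protocol 9.8.3 counts permanent discontinuation of study medication within the 30%. A reader might set 13 patients against the 360 evaluable (13/360 = 3.6%) and infer a matching shortfall. The documents do not support that: late stoppers belong to the 156 (520 − 364) already written off. This objection stands in full.

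**The count is generous.** The 30% also covers death, loss to follow-up and start of AD treatment. The first two leave no EOS visit to waive, and scores after AD treatment starts are outside the primary analysis anyway. EOT may also be held up to three months after the last dose, so for some patients it falls at or near Month 36 and the battery is done then. This stands too, which is why 11 to 13 is a ceiling.

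**A nearby battery exists and might be remapped.** This stands in part. Protocol 9.4.3 leaves the possibility open, and SAP Section 4 declares no change to protocol-specified analyses. But permission that may not cover EOT visits, with no matching SAP rule, is not a planned use of the value.

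**PET and MRI.** A reader might infer that the 3-year scan is wrongly cancellable as well, for instance after a late Month 18 scan. The documents do not support calling that an error. Footnote 5, Section 6 and Section 6.5.1 agree, and the Amendment 1 summary shows that the 6.5.1 rule was set on purpose. Section 3.1 has its own 12-month waiver. On schedule the gap is 156 − 78 = 78 weeks. The SUVr imputation uses actual scan time and all on-treatment scans. The SAP's "wider assessment window extending from 6 months to 9 months for assessments that are scheduled to take place starting Mar 1, 2020 and onwards" belongs to one supportive analysis and does not authorise late scanning. What remains is a difference in trigger: an EOT scan in Section 3.1, any scan within 12 months elsewhere.

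None of this removes the CCB and FAQ contradiction.

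**Conclusion.** The protocol contradicts itself on whether the CCB and FAQ at Visit 299 are conditional. Read literally, the table and Section 6 cause a Week 156 assessment to be skipped in a small group, mainly late discontinuers with an EOT battery after about Week 143. Some of those scores would have been eligible for the primary analysis, and all would have entered the FAS analysis.

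The size is small: at most about 11 to 13 of 520 for primary-eligible scores. That rests on the 30% loss being spread evenly or exponentially over 36 months and on 13 weeks standing for three months. The stated sample size and power are unaffected.

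The heading could tempt a reader to conclude that the primary endpoint assessment is generally at risk. It is not, because a patient seen on schedule always has it. The point is worth acting on because the loss is avoidable and the two sets of instructions cannot both be followed.

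**What to change.** - **Footnote 6 of Table 6-1:** remove EOS, so that the three-month condition applies to EOT only.
- **Section 6:** the CCB and FAQ sentence takes its scope from the sentence before it, which names both visits. Reword it to name EOT alone. The CCB and FAQ are then always done at Visit 299, as Sections 6.4.1 and 6.4.4 already say.
- **SAP 2.5.3:** for any Week 156 assessment already skipped, state before database lock whether an EOT battery near Week 156 may stand in for it.
- **PET and MRI:** reconcile the waiver trigger between Section 3.1 and footnote 5, Section 6 and Section 6.5.1. No particular rule is proposed here.

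The cost is amendment wording and one repeat battery and FAQ, within about three months of the last, in a few patients. Short-interval repetition is already part of the design: the battery is given at screening, Visit 103 and randomization, and Section 3.2 describes it as having minimal practice effects.
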